3.0 Intervention to be studied (if applicable)

We will utilize a floating electrode-dielectric barrier device (FE-DBD) Cold atmospheric plasma (CAP) device on molluscum and warts in children and adolescents 4-21 years (Figure 1). Children and adolescents are targeted because they are the population most affected by painful standard of care therapy. The study will continue until at least 68 warts and 68 molluscum are treated. Each patient will not have more lesions treated than SOC recommendations. Half the lesions will be treated with plasma and the other half with standard of care being cryotherapy for warts and cantharidin for molluscum. A single patient must have minimum of 1 clinically diagnosed lesion treated and maximum of 20 treated. Lesions with a clinical impression of warts or molluscum will be selected. Selection of treatment type (control vs NTAP) will be randomly selected. Lesions

Page 3 of 13

The treatment device in this study generates cold atmospheric plasma. Cold atmospheric plasma has certain properties of plasma, such as ionized gas molecules. To create plasma, a pulse generator supplying 20-kV pulse of 20-ns pulse width at 200 Hz (FPG10-01NM10, FID GmbH, Burbach, Germany) to a 5-mm diameter quartz-covered copper electrode of 10-cm length and 1-mm quartz thickness (5). These nanosecond pulse parameters were chosen to provide sufficient treatment dose at the high level of plasma uniformity required to avoid any tissue damage. We treated the lesions for approximately 1 to 2 minutes each, moving the electrode gently over the treatment area.

After the study treatments are completed, we will analyze the data to see if the treatment was safe and effective.

Non-significant risk device statement (6-19) (Figure 1)

- We are proposing a clinical trial floating electrode-dielectric barrier device (FE-DBD) a Cold Atmospheric Plasma (CAP) device.
- While novel to the medical field and especially to dermatology, there are already a number of publications regarding its use on human skin in adults (20-26) and children (29).
- CAP devices utilize noble gases (such as helium) to deliver plasma state matter to the skin. As
 its name implies, the generated plasma stream is of near skin temperature and it exists on
 normal atmospheric pressure. During the generation of the plasma there is no electric contact
 with the patient. The treatment does not increase skin surface temperature and the used helium

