1.0 Study Endpoints (if applicable)

- Clinical assessment response after 4, 8 or 12 weeks. This will be assessed by a blinded study team member comparing clinical photographs and dermascopic images.
 - Clinical photographs measured by no response, partial resolution, complete resolution.
 - Dermoscopy images: no response, partial resolution, complete resolution using the guidelines below that indicate the presence of wart or mollusum.
 - Molluscum: Visualization of a central umbilication with polylobular, white to yellow, amorphous structures is typical. A peripheral crown of radiating or punctiform vessels is also present.
 - Wart: grouped papillae, with dotted or loop vessels, and/or hemorrhagic points and lines often surrounded by a whitish halo
- Visual analogue scale for experimental treatment and control treatment
 - The visual analogue scale (VAS) is a validated subjective measurement of pain experienced by the patient. It consists of visual-numeric scale, numbered from 0-10. (0) indicate absence of pain or "no pain at all", while (10) indicates severe pain or "worst imaginable pain". This is supplemented by six faces with different expressions, ranging from happy to extremely upset. Each facial expression is assigned a numerical scale from 0 to 10.
- Evaluation of tolerability included assessment of dry ness, peeling, scaling, erythema, edema, stinging, burning sensation, itching, scaring and dyspigmentation. They will be assessed by means of a standardized grading scale (0 = absent; 1 = mild; 2 = moderate; 3 = severe)

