6.0 Number of Subjects

Total of 150 would be required (half control, half NTP) to achieve 80% power with an alpha of

.05.

Calculation:

- Assumption for Probabilities for the Null hypotheses is P1=P2=P3=1, hence P1 = .333333, P2 = .333333, P3 = .333333 and P1+P2+P3 = 1.0 or that each proportion has an equal chance.
- Assumption for Probabilities for Alternative Hypothesis is taken from Provided NTP paper where P1=9/17 (Full Resolution = .53), P2=3/17=.18 (Some Improvement), and P3=5/17=.29 (no improvement).

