- Patient will return to the office for a 4-week standard of care follow-up. Study cessation or additional treatment will be determined by the provider assessment of lesion clearance. If lesion persist another treatment will occur. No greater than 3 treatments will be performed.
- This study will be single blinded, meaning the study team member accessing the results will
 not know which lesions were treated with what therapy. Assessment of clearance will be based
 off of clinical examination and images. The team will record any additional clinical feature
 that may arise during the analyses.

11. Data Management

- Continuous data will be summarized using descriptive statistics (number of values, means, standard deviation, median, minimum and maximum). Categorical data will be summarized using frequency tables (frequencies and percent).
- Chi-square analysis comparing the proportions of successes (equal chance outcomes).
- Coded dermoscopic and clinical photographs may be obtained for further analyses after each visit. Files with patient images will be stored in a secure departmental drive that will only be accessible to study team members by their unique MUSC ID and password.
- All subject medical record information and data collection will be coded and stored on an MUSC Box drive only accessible to study team members and will be protected by two-factor authentication. The linking document between ID and PHI will be maintained separately from the study data in a separate encrypted folder.

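### The only planned test most likely ignores the order of the none/partial/complete grades, so by itself it shows neither which treatment clears more lesions nor that the two are equally effective

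*Combined protocol and SAP*

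**What the plan says.** The Study Endpoints section uses the same three grades for both image types: "Clinical photographs measured by no response, partial resolution, complete resolution", and "Dermoscopy images: no response, partial resolution, complete resolution using the guidelines below". These grades run from worst to best.

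Section 11 (Data Management) names one inferential method: "Chi-square analysis comparing the proportions of successes (equal chance outcomes". The rest of its analysis wording is descriptive. The documents do not define success, assign scores to the grades, or mention a trend, rank or ordinal method. No effect estimate or confidence interval is planned.

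Section 6 sets up its calculation on three category probabilities. The null is "hence P1 = .333333, P2 = .333333, P3 = .333333 and P1+P2+P3 = 1.0 or that each proportion has an equal chance", and the alternative is "P1=9/17 (Full Resolution = .53), P2=3/17=.18 (Some Improvement), and P3=5/17=.29 (no improvement". The stated size is "Total of 150 would be required (half control, half NTP) to achieve 80% power with an alpha of" .05. Section 3 sets a different target: "The study will continue until at least 68 warts and 68 molluscum are treated".

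The hypothesis in the Objectives section is that NTAP is as effective as the comparator and painless.

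**The concern.** A chi-square on a 2 x 3 table treats the three grades as unordered labels. It asks whether the two distributions differ in any way, including in spread. The trial asks something else: whether NTAP clears lesions as well as standard of care (SOC), and by how much it does better or worse.

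Two consequences follow. A small p-value could come from more lesions at both extremes on one arm, and the test would not say which arm is preferable. A large p-value could be taken as support for equal effectiveness, although no estimate or interval is planned to show what differences remain possible. Because success is undefined, the choice between a three-grade and a two-grade test, and of the cut-point, could also be made after the results are seen.

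**Working it through.** **Which test is meant.** Section 11 speaks of successes, which suggests two categories. Its equal-chance wording repeats the Section 6 null of one third per grade, which suggests three. The three-category reading is better supported but not certain.

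The sample size does not settle it. A 2-df chi-square at alpha .05 needs a noncentrality of 9.635 for 80% power.
- One sample against thirds: w² = 3 × Σ(p − 1/3)² = 0.194, so N = 9.635/0.194 ≈ 50.
- Two arms, with thirds used as the SOC arm: Σ(p − q)²/(p + q) = 0.00245 (none) + 0.04827 (partial) + 0.04456 (complete) = 0.0953, so n = 9.635/0.0953 ≈ 101 per arm, about 202 in total.
- Complete resolution only, .53 v .333, two-sided: 99 per arm.

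None of these gives 150. A one-sided unpooled two-proportion formula gives 76 per arm (152), but the documents state neither a one-sided test nor a binary outcome.

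**Inputs for the checks.** 75 v 75 comes from Section 6 (150, halved). 34 v 34 per lesion type comes from Section 3 (68, halved). The SOC rates are assumptions. Lesions are treated as independent and tests are two-sided at .05. With n per arm, noncentrality is n × Σ(p − q)²/(p + q).

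**Check 1: same mean grade, different spread.** NTAP is 35/30/35% and SOC is 25/50/25% (none/partial/complete). With scores 0, 1, 2 the means are 0.30 + 2 × 0.35 = 1.00 and 0.50 + 2 × 0.25 = 1.00. The sum is 0.10²/0.60 + 0.20²/0.80 + 0.10²/0.60 = 0.0833.
- At 75 v 75, noncentrality is 6.25 and power is 60% (about 61% by simulation).
- At 34 v 34, noncentrality is 2.83 and power is 31% (31 to 32% by simulation).
- Ordered tests reject in about 5%.

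**Check 2: consistent shift.** Assume SOC at thirds and a common odds ratio of 2.25. The odds of complete resolution become 0.5 × 2.25 = 1.125 (53%). The odds of any improvement become 2 × 2.25 = 4.5 (82%). NTAP is then 18/29/53%. The sum is 0.0923; × 75 = 6.92, giving 65% power (66% by simulation).

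**Check 3: the plan's own alternative against assumed thirds.** 0.0953 × 75 = 7.15, giving 66% power (67 to 68% by simulation). Of the noncentrality, 51% comes from partial, 47% from complete and 3% from none. The odds ratios are (9/8)/0.5 = 2.25 for complete resolution and (12/5)/2 = 1.2 for any improvement, so this is not a consistent shift.

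Simulated power at 75 v 75:

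| Test | Check 2 | Check 3 |
|---|---|---|
| 2 x 3 chi-square | 66% | 67% |
| Complete v rest | about 70% | about 70% |
| Wilcoxon | 76% | 43% |
| 0/1/2 mean score | about 75% | 39% |

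**Check 4: what a non-significant result leaves open.** Suppose both arms show one third complete resolution. The 95% CI for the difference has half-width 1.96 × √(2 × 0.333 × 0.667/n). That is about 15 percentage points at n = 75 and about 22 at n = 34. No observed difference at all would still allow gaps of that size.

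**The case against.** The strongest objection is that Section 11 refers to successes, which is the language of a binary outcome. On that reading the test has 1 df and a direction, and the cost of merging grades is small: about 70% v 76% even in the scenario that favours an ordered test. This stands. It narrows the point, but it also shows that success must be defined.

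Two stronger inferences are tempting, and the documents support neither.
- A reader might infer that the chi-square gives false positives when neither treatment is better. It does not. With identical arms it rejects in about 5% of simulated trials. In Check 1 the distributions really differ, and complete resolution is 35% v 25%. The arms tie only if a partial response counts as half a complete one. Section 10 bases stopping or further treatment on lesion clearance, so another weighting is defensible.
- A reader might infer that an ordered test should replace the chi-square because it has more power. That holds for a consistent shift (76% v 66%). At the plan's own 9/17, 3/17, 5/17 against assumed thirds it is reversed: 39 to 43% v 67%, a loss of 24 to 28 points.

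Nor do the Section 6 thirds describe an SOC arm. They are a null hypothesis, and using them as SOC rates is an assumption made here.

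**Conclusion.** The concern holds in a limited form. On the better-supported reading, the sole planned test has no direction. A significant result would not identify the better treatment, and a non-significant one would not show equal effectiveness. The size is illustrated by about 61% rejection at 75 v 75 (31 to 32% at 34 v 34) when mean grade is equal but spread differs.

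The test is valid for detecting any difference between independent samples, so this is a mismatch with the question and not an error-rate failure. The documents do not establish that an ordered test would be the better primary analysis. Complete v rest keeps direction and has about 70% power in both the consistent-shift scenario and the plan's own.

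All power figures rest on independent lesions and assumed SOC rates. Section 3 allows 1 to 20 treated lesions per child, so a child-adjusted analysis would give different values, which were not calculated.

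**What to change.** In Section 11:
1. Define success as complete resolution, and name the image reading and visit to which this applies.
2. Make the primary result the NTAP-minus-SOC difference in complete resolution with a 95% CI that accounts for child, as stratum or cluster. If child is a stratum, place children with a single lesion together in one stratum, since they provide no within-child comparison.
3. Keep the 2 x 3 table as description.
4. Add one ordered analysis as support, not as a replacement: a cumulative-logit model with child as cluster, or a row-mean-score test stratified by child. State beside it that it gains about 10 points under a consistent shift and loses about 24 to 28 at the plan's own figures against assumed thirds.

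The interval shows which differences remain possible. A formal claim of equal effectiveness would also need a margin fixed in advance, and the documents give none.

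The cost is a few sentences and standard software, with no new data or patients. Moving from the 2 x 3 chi-square to complete v rest loses no power at the plan's figures (about 70% v 67%). The change should be made before outcomes are compared by treatment.

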14.0 Withdrawal of Subjects (if applicable)

• Patient may withdraw at any time. Subjects may verbally notify investigators if they wish to voluntarily withdrawal from the study immediately. All data collected until this point will be retained for study purposes.

15.0 Risks to Subjects

Risk for NTAP: To date, there are no known side effects or risks associated with the use of cold atmospheric or studies producing discomfort or pain (20-26, 29). However, because this is an experimental device, side effects like blistering, scarring, significant pigmentary alteration, and/or persistent nail change could occur and will be monitored at each visit, as well as pain assessment at every treatment session by validate pain scale (VAS).

The treatment received may prove to be less effective or to have more side effects than the other study treatment(s) or other available treatments.

This is a new device and even though no side effects of this treatment are reported in literature to date (27), the IRB will be notified via amendment, as well as participants via phone call if one arises.

There is a risk for possible breach of confidentiality. However, all measures to keep information protected will be taken. Photographs will be stored in the coded study-specific medical record for further analysis of lesion features. Only study team members will be able to access.

A cumulative data assessment will be conducted every other month throughout the study's duration by study team members. A report that includes any available efficacy data, as well as a record of anticipated adverse events, can be compiled and submitted to the IRB at that time. Any event meeting the criteria of an unanticipated problem involving risks to subjects or others will be immediately reported to the MUSC IRB, as required by HRPP 4.7- Unanticipated Problems and Adverse Events Policy and Procedures.

The plan for subject safety and minimizing risks of the research is assessing AE during, immediately following treatment and a few days after. Participants are encouraged to reach out to the study team if they think they are experiencing any adverse events. Other expected adverse effects deemed intolerable by the patient will prompt reduction in the patient's frequency, duration and treatment if indicated. Any condition necessitating cessation of the study drug will be followed to resolution.

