Multiple modes of NTAP, also known as cold atmospheric plasma (CAP), have been employed in dermatologic clinical studies such as wound healing, onychomycosis, actinic keratosis and viral warts (28). Friedman's case series on warts proved it safety and efficacy in children, reporting no adverse events (blistering, scarring, significant pigmentary alteration or persistent nail changes) or pain reported in treatment (29). A proof-of-concept study on warts in children demonstrated efficacy and exceptional tolerability when treated with plasma as a result of its intracellular calcium influx and viral replication inhibiting effects. In actinic keratosis they had a 70% improvement rate with no discomfort during or after treatment. Onychomycosis had a 50% clinical and 15% mycological cure rate in 13 patients without any side effects. And wound healing of chronic ulcers had decreased bacterial as expected from well-documented inhibitory effects on bacteria and also superior wound healing rates compared to wound care alone. Moreover, it has been shown to be safe and successful in proof-of concept studies exploring its application in the treatment of Verruca vulgaris. Its efficacy in molluscum has not yet been tested.

Given NTAP's outstanding safety profile and painless application (5), its prior proof of concept success in treating common verrucae, and the similarity between verrucae and molluscum, we propose to use NTAP to treat these conditions and expand upon the existing research literature.

If the NTAP device is shown to be a successful, efficacious and painless treatment option for children and adolescents with verrucae and molluscum, this would be a revolutionary and environmentally friendly approach to two of the most common viral infections and chief complaints found during dermatology visits in this age group. The non-toxic, chemical free, waste free, multi-year device results in a significant reduction of effluents, which is beneficial from an economic but also an environmental viewpoint (30).

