10.0 Study Design / Methods

- A chart review of patient the patient's medical record will be completed and the following information will be collected for research purposes: DOB, demographics, contact information and diagnosis.
- Skin irritants, emollients, topical medications and other topical products cannot be applied to the study area 4 weeks prior to the start of the study and throughout the duration of the study. Details of what can and cannot be used can be discussed any time.
- During a clinical care visit, if a patient is eligible and agrees to participate, lesions will be selected by the dermatologist prior to procedure. The lesions will be marked randomly for a certain treatment regimen and photographs will be taken before each treatment and after completion of the study. Identifiers will be covered to protect identity. All images will be saved on a MUSC network secure box drive using a subject study number.
- The number of lesions treated will not exceed SOC recommendations. They will be determined by provider assessment and anatomical location.
- Participants with one lesion will receive either NTAP or standard of care (SOC). SOC is

Page 8 of 13

cryotherapy for warts and cantharidin for molluscum. Participants with greater than 2 lesions will receive equal treatment of NTAP and SOC. The number of lesions treated will be based off the providers assessment and anatomical location. Treatment of a single lesion or an odd number of multiple lesions will be based off a randomized list.

- All SOC lesions will be treated first to reduce the number of patients not wanting return to the more painful modality.
- All people in the room will be provided eye shields that must be worn during treatment. The patient will be placed in a comfortable position before the lesion is cleaned with alcohol.
- Each lesion will be treated for 1-2 minutes. Total treatment duration will be no longer than 20 minutes.
- The interval between treatment groups will about 1 minute.
- There will be a follow-up phone call a week after treatment to check on resolution and report any adverse events. If an adverse event is reported the study team members will access if the patient needs to be seen by a provider that day.

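### Blistering and persistent nail change are to be monitored but are not on the graded tolerability scale, and the plan does not tie them to a lesion or to the standard-of-care arm

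*Combined protocol and SAP*

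**What the plan says.** Section 15.0 (Risks to Subjects) opens its device paragraph with "Risk for NTAP: To date, there are no known side effects or risks". It then allows that, because the device is experimental, "side effects like blistering, scarring, significant pigmentary alteration, and/or persistent nail change" "could occur and will be monitored at each visit". The paragraph gives no severity grade and no rule for recording by lesion. No matching paragraph covers cryotherapy or cantharidin.

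The same four harms appear in section 2.0 (Background), where an earlier paediatric wart case series is reported to have seen none of them: "blistering, scarring, significant pigmentary alteration or persistent nail changes".

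The Study Endpoints section sets out the graded measure: "Evaluation of tolerability included assessment of dry ness, peeling, scaling, erythema, edema, stinging, burning sensation, itching, scaring and dyspigmentation". Each item is scored "0 = absent; 1 = mild; 2 = moderate; 3 = severe".

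Adverse events are also sought by telephone under section 10.0 (Study Design / Methods): "There will be a follow-up phone call a week after treatment to check on resolution and report any adverse events". Section 15.0 adds adverse event checks during treatment, straight afterwards and a few days later. Under section 10.0, participants with several lesions have them divided between plasma and standard of care, with about one minute between the two groups of treatments.

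**The concern.** The plan names the harms it thinks the device might cause, then builds its graded tolerability measure from a list that leaves out two of them. Those two fall to general monitoring, for which the plan states no grade and no link to a lesion. The one sentence that names them sits in a paragraph about plasma risk.

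The lesion link matters because of the within-participant allocation. If a child has plasma on some lesions and cryotherapy or cantharidin on others minutes apart, a note that the child had a blister does not say which treatment preceded it. What is at stake is whether the final report can set the two treatments side by side on these harms, and with what severity. If staff looked for blistering more carefully on plasma lesions than on control lesions, the resulting counts could also be tilted against the device, so the sponsor has its own reason to settle this.

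**Working it through.** The plan has no figure to reproduce here. The check sets the two lists side by side and then asks what each other source of harm data would supply.

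**Step 1. Compare the lists.**

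| Harm named in section 15.0 | On the 0 to 3 scale in Study Endpoints? |
|---|---|
| Blistering | No |
| Scarring | Yes (spelled with one r) |
| Significant pigmentary alteration | Yes (as dyspigmentation) |
| Persistent nail change | No |

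The scale has ten items: dryness, peeling, scaling, erythema, edema, stinging, burning, itching, scarring and dyspigmentation. Two of the four named harms are covered and two are not. None of the ten stands in for the missing two: edema, peeling and scaling are different signs from a blister, and no item concerns nails. Nail change can arise in this population, because section 5.0 excludes only face and genital sites, which leaves lesions near nails eligible.

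**Step 2. Go through the other sources.**

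- *Visit monitoring (section 15.0).* It names both harms. It gives no grade and no lesion rule, and it is written under plasma risk.
- *Adverse event checks during treatment, straight after and a few days later (section 15.0), and the one-week call (section 10.0).* These are not restricted to one arm. They are not tied to a lesion either.
- *Photographs (section 10.0).* These are by lesion and cover both arms. They are taken before each treatment and at the end of the study, so a blister that came and went between two photographs would not be shown.
- *Recording of additional clinical features (section 10.0).* This is open-ended and attached to the assessment of clearance. It does not require anyone to look for a particular harm.
- *Frequency tables for categorical data (section 11).* These can be split by arm only if the event was recorded against a lesion.

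**Step 3. Ask when the arm is recoverable.** For a participant with one treated lesion, a participant-level report is enough, because only one treatment was given. For a participant with lesions in both groups, the report identifies the arm only if someone notes the lesion. No section requires that for blistering or nail change.

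**Step 4. Conclude.** No source yields a severity grade for the two harms. Several could yield a yes/no count by arm, provided that staff record the lesion and examine control lesions in the same way. The plan requires neither.

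**The case against.** A reader might infer that the arms cannot be compared at all on blistering and nail change. The documents do not support that. The harms are to be monitored, the adverse event checks and the telephone call are not limited to plasma lesions, lesions are marked for treatment and photographed, and categorical data go into frequency tables. A count by arm is possible; it is only not assured.

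A reader might also infer that control lesions will not be examined for these harms. The sentence does stand under the plasma heading, but that paragraph is a statement of risk, and the plan is silent on control lesions without excluding them.

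Third, the safety aim should not be described as an explicit comparison. Section 1.0 (Objectives / Specific Aims) speaks of the safety profile and tolerability of the treatment, in the singular, and its reference to each treatment can mean each session. Only the pain scale is stated for both the experimental and the control treatment. Against this, section 15.0 does warn that the treatment received may turn out to have more side effects than another study treatment, so a difference between arms is contemplated.

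Finally, neither list is clearly closed: the risk paragraph gives examples, the tolerability sentence says what assessment included, and grading some signs while leaving others to adverse event reporting is a legitimate design choice.

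These points limit the consequence. They do not supply a grade, a lesion identifier or a statement that both arms are handled alike.

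**Conclusion.** The point holds in limited form. Two of the four harms named in section 15.0 are missing from the ten-item graded scale, and the plan does not say they are recorded per lesion or for standard-of-care lesions. A graded comparison on those two is not provided for, and a comparison of counts by arm is not assured. The two-of-four tally describes the lists only; it says nothing about how often the harms occur or how large any bias would be, and the documents give no figures for either.

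The conclusion assumes that the Study Endpoints list is what the graded form would contain; the form itself is not in the documents. If the working form already has these items by lesion for both arms, the plan needs only to say so. The matter is minor, a cheap improvement to data collection, and no analysis or sample size depends on it.

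**What to change.** Add blistering and nail change to the graded list in Study Endpoints, with nail change scored only where a treated lesion is near a nail. State that the whole scale is graded per lesion, identically for plasma and standard-of-care lesions, at each office visit. Recording by lesion number lets the treatment be attached at analysis. At the one-week call, do not grade the scale; note only which treated lesion a reported adverse event concerns. Grading everything by telephone is unnecessary, and whether a nail change persists cannot be judged at one week.

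The cost is more recording at visits for participants with many lesions. Section 3.0 allows up to 20 treated lesions. With twelve items the ceiling is 20 × 12 = 240 grades at a visit, against 20 × 10 = 200 if the present ten items were graded per lesion. The added items therefore account for at most 40 grades, fewer where nail change does not apply. If the scale is now scored once per participant, most of the extra work comes from moving to per-lesion grading. For a participant with one lesion the change is at most two extra entries.
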